Dose Level	BMS-986156 Part A and Part B	Nivolumab Only Part B
-1	3 mg	240 mg IV Q2W
1	10 mg	240 mg IV Q2W
2	30 mg	240 mg IV Q2W
3	100 mg	240 mg IV Q2W
4	240 mg	240 mg IV Q2W
5	800 mg	240 mg IV Q2W

Abbreviations: IV, intravenous; MAD, maximum administered dose; MTD, maximum tolerated dose; PK, pharmacokinetics; Q2W, every 2 weeks.

¹ Babb 1998; Neuenschwander 2008.

- a Additional subjects may be added for a total of up to 12 subjects per selected dose levels to provide additional safety, tolerability and PK data. This information will be incorporated into final recommendation for MAD/MTD/alternate dose(s) of BMS-986156
- b Dose -1 (3 mg) will be evaluated if 10 mg (dose level 1) exceeds MTD
- c Starting dose for Part B will be one dose level lower than a dose already tested and shown to be tolerated in ongoing monotherapy dose escalation in Part A ([Section 1.1.4](#) for details)

Cohort Expansion (Parts C, D, and E): The purpose of cohort expansion is to gather additional safety, tolerability, preliminary efficacy, PK [REDACTED] information regarding BMS-986156 as monotherapy or in combination with nivolumab.

Continuous evaluation of toxicity events in the cohort expansions will be performed throughout enrollment in the expansion cohorts. If, at any time, the aggregate rate of treatment-related toxicities meeting DLT criteria exceeds 33% across all subjects treated in the Part C cohort expansions, the findings will be discussed and further enrollment may be interrupted. Depending on the nature and grade of the toxicity and after assessing the risk: benefit ratio, a new dose(s) for all cohorts may be initiated at a previously tested lower dose level or at a dose level intermediate to previously tested lower dose levels.

Part C consists of cohort expansions with BMS-986156 monotherapy in 2 disease-restricted populations: (i) NSCLC subjects with progressive or recurrent disease (per RECIST v1.1) during or after anti-PD-1 or anti-PD-L1 therapy following prior platinum doublet-based chemotherapy and (ii) persistent, recurrent or metastatic cervical cancer.

Part D consists of cohort expansion with BMS-986156 administered in combination with nivolumab in disease-restricted populations as follows: (i) NSCLC, (ii) cervical, (iii) bladder cancer, (iv) squamous cell carcinoma head and neck, (v) ovarian cancer, and (vi) hepatocellular carcinoma.

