Part D consists of cohort expansion with BMS-986156 administered in combination with nivolumab in disease-restricted populations as follow: (i) NSCLC, (ii) cervical, (iii) bladder cancer, (iv) squamous cell carcinoma head and neck, (v) ovarian cancer, and (vi) HCC, of approximately 40 subjects each.

[figure not shown]
Part E consists of cohort expansion with BMS 986156 administered in combination with nivolumab in cervical cancer (cohort 9) and other tumor types (Cohort 10). Each cohort will contain approximately 40 subjects each. Patients who discontinue for reasons other than disease progression, death, or treatment-related toxicity may be replaced.

No more than 5 subjects previously found to be “rapid progressors” on anti-PD-1 or anti-PD-L1 therapy will be enrolled per cohort. Rapid progressors are defined as subjects who have progressed as of their first response assessment while on prior PD-1/PD-L1 therapy (if applicable).

Cohort expansion arm in part C will consist of approximately 25 subjects. Cohorts in Part D and Part E will contain approximately 40 subjects. Patients who discontinue for reasons other than disease progression, death, or treatment-related toxicity may be replaced. Treatment in Parts C and D will be initiated when the MTD/MAD/alternate dose(s) for monotherapy and combination with nivolumab have each been determined based on evaluation of the totality of available clinical safety, PK, [REDACTED] and modeling data for Parts A and B, respectively. The doses selected for Parts C, D, and E will not exceed the MTD or MAD determined in Parts A and B. Part D may begin while Part B continues to explore higher dose levels.

A schematic of the study is provided in [Figure 3.1-1](#).

Figure 3.1-1: Study Schematic

Part E
Cohort Expansion
BMS-986156 + nivolumab

Cohort 9:
Ca Cervix: \geq 2L metastatic/recurrent

Cohort 10:
**Other solid tumor types NSCLC, HCC,
SCCHN, ovarian, Bladder –**

Subjects will complete up to 3 phases of the study: Screening, Treatment, and Safety follow-up, as described below:

Screening

The screening phase will last for up to 28 days. Screening phase begins by establishing the subject's initial eligibility and signing of the ICF. Subjects will be enrolled using the Interactive Voice Response System (IVRS).

Treatment Phase

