Continuous evaluation of toxicity events in the cohort expansions will be performed throughout enrollment in the expansion cohorts. If at any time, the aggregate rate of treatment-related toxicities meeting DLT criteria exceeds 33% across all subjects treated across all cohorts treated within monotherapy and combination therapy phases at the same dose, the findings will be discussed and further enrollment may be interrupted. Depending on the nature and grade of the toxicity and after

assessing the risk/benefit ratio, a new dose(s) for all cohorts may be initiated at a previously tested lower dose level or at a dose level intermediate to previously tested lower dose levels.

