3.7 Stopping Rules During Cohort Expansions

Continuous evaluation of toxicity events in the cohort expansions will be performed throughout enrollment in the expansion cohorts. If at any time, the aggregate rate of treatment-related toxicities meeting DLT criteria exceeds 33% across all subjects treated across all cohorts treated within monotherapy and combination therapy phases at the same dose, the findings will be discussed and further enrollment may be interrupted. If an expansion cohort is discontinued due to toxicity, a new cohort at a previously tested lower dose level, or an alternate treatment regimen (see [Table 3.4.1-1](#)) may be considered based on the aggregate safety experience and in consultation and agreement between Investigators and Sponsor.

All safety signals throughout the conduct of the study will be reviewed by the BMS-986156 Medical Surveillance Team (MST). If unexpected safety findings are identified between scheduled MST meetings, an ad hoc meeting will be convened as appropriate.

Efficacy and safety will be continuously monitored and go/no go decision will be made by discussion with sponsor based on totality of data after assessing benefit/risk ratio in combination with clinical judgement.

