- 1) White blood cell $\geq 2000/\mu\text{L}$ (stable off any growth factor within 4 weeks of first study drug administration)
- 2) Neutrophils $\geq 1500/\mu\text{L}$ (stable off any growth factor within 4 weeks of first study drug administration)
- 3) Platelets $\geq 100 \times 10^3/\mu\text{L}$ (transfusion to achieve this level is not permitted within 2 weeks of first study drug administration) subjects with hepatocellular cancer $\geq 60 \times 10^3/\mu\text{L}$
- 4) Hemoglobin $\geq 8.5 \text{ g/dL}$ (transfusion to achieve this level is not permitted within 2 weeks of first study drug administration)
- 5) Alanine aminotransferase (ALT) and aspartate aminotransferase (AST) $\leq 3x \text{ ULN}$ subjects with hepatocellular cancer $\leq 5x \text{ ULN}$

- 6) Total bilirubin $\leq 1.5 \times$ ULN (except subjects with Gilbert's Syndrome who must have normal direct bilirubin) subjects with hepatocellular cancer Bilirubin < 3 mg/dL
- 7) Normal thyroid function or stable on hormone supplementation per Investigator assessment
- 8) Serum creatinine $\leq 1.5 \times$ ULN or creatinine clearance (CrCl) ≥ 40 ml/min (measured using the Cockcroft-Gault formula below):
Female CrCl =
$$\frac{(140 - \text{age in years}) \times \text{weight in kg} \times 0.85}{72 \times \text{serum creatinine in mg/dL}}$$

Male CrCl =
$$\frac{(140 - \text{age in years}) \times \text{weight in kg} \times 1.00}{72 \times \text{serum creatinine in mg/dL}}$$
- 9) Albumin > 2.8 mg/dL
- 10) Ability to comply with treatment, PK [REDACTED] sample collection, and required study follow-up.
- 11) Subject Re-enrollment: This study permits the re-enrollment of a subject that has discontinued the study as a pre-treatment failure (e.g., subject has not been treated). If re-enrolled, the subject must be re-consented.

3) Age and Reproductive Status

- a) Men and women, ages ≥ 18 years at the time of informed consent
- b) Women of childbearing potential (WOCBP) must have a negative serum or urine pregnancy test (urine pregnancy test: minimum sensitivity 25 IU/L or equivalent units of human chorionic gonadotropin [hCG]) within 24 hours prior to the start of study drug.
- c) Women must not be breastfeeding.
- d) WOCBP must agree to follow instructions for method(s) of contraception for the duration of treatment with study drug (s) plus 5 half-lives of study drug plus 30 days (duration of ovulatory cycle) for a total of 23 weeks post-treatment completion.

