4.3.1 Dose-limiting Toxicities

AEs will be graded according to the NCI CTCAE v4.03.

Non-hematologic Dose-limiting Toxicity (DLT)

A. Hepatic Non-hematologic DLT

Any one of the following study drug-related events will be considered a hepatic DLT:

- Any Grade ≥ 3 elevation of AST, ALT, or total bilirubin
- Grade 2 AST or ALT with symptomatic liver inflammation (e.g., right upper quadrant tenderness, jaundice, pruritus)
- AST or ALT $> 3 \times$ ULN and concurrent total bilirubin $> 2 \times$ ULN without initial findings of cholestasis (elevated serum ALP (e.g., findings consistent with Hy's law or FDA definition of potential drug-induced liver injury or pDILI). Note that this special category of DLT uses ULN rather than CTC Grade for definition

B. Non-hepatic Non-hematologic DLT

Any of the following events will be considered a Non-Hepatic Non-Hematologic DLT:

- Any Grade 2 drug-related uveitis or eye pain or blurred vision that does not respond to topical therapy and does not improve to Grade 1 severity ≤ 2 weeks OR requires systemic treatment
- Grade 3 drug-related uveitis, pneumonitis, bronchospasm, neurologic toxicity, hypersensitivity reaction, or infusion reaction of any duration requires discontinuation
- Any Grade 3 or greater non-dermatologic, non-hepatic non-hematologic study drug-related toxicity will be considered a dose-limiting toxicity with the following specific EXCEPTIONS:
 - Grade 3 or grade 4 electrolyte abnormalities that are not complicated by associated clinical adverse experiences, last ≤ 48 hours and either resolve spontaneously or respond to conventional medical intervention
 - Grade 3 nausea, vomiting or diarrhea that lasts less than 48 hours, and either resolves spontaneously or responds to conventional medical intervention
 - Isolated Grade 3 elevation of amylase or lipase not associated with clinical or radiographic evidence of pancreatitis
 - Isolated Grade 3 fever not associated with hemodynamic compromise (eg, hypotension, clinical or laboratory evidence of impaired end-organ perfusion)
 - Grade 3 endocrinopathy that is well controlled by hormone replacement
 - Grade 3 tumor flare (defined as pain, irritation, or rash that localizes to sites of known or suspected tumor)
 - Grade 3 fatigue for ≤ 7 days
 - Grade 3 infusion reaction that returns to Grade 1 in ≤ 6 hours

C. Dermatologic DLT

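### The only numerical toxicity trigger for the expansions is an aggregate over cohorts, so at full enrolment one badly affected Part D cohort would be diluted below 33%

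*Combined protocol and SAP*

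**What the plan says.** Sections 3.5 and 3.7 state the same rule. Toxicity in the expansion cohorts is evaluated continuously. If at any time the aggregate rate of treatment-related toxicity meeting the DLT criteria "exceeds 33% across all subjects treated across all cohorts treated within monotherapy and combination therapy phases at the same dose", the findings are discussed and enrolment may be interrupted. No minimum number of subjects is given, and no threshold for a single cohort or tumour type.

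The synopsis (Cohort Expansion) uses a different denominator: the rule applies when the rate "exceeds 33% across all subjects treated in the Part C cohort expansions". Read literally, that leaves Parts D and E without a numerical trigger.

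Section 3.7 then provides for action on one cohort: "If an expansion cohort is discontinued due to toxicity, a new cohort at a previously tested lower dose level", or an alternate regimen, may be considered. It does not say what toxicity rate would lead to that.

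Section 3.1 lists the Part D cohorts as "i) NSCLC, (ii) cervical, (iii) bladder cancer, (iv) squamous cell carcinoma head and neck, (v) ovarian cancer, and (vi) HCC, of approximately 40 subjects each", and the synopsis gives them one combination dose. Part E uses a different dose and schedule. In Appendix 1, Section 3.1, 33% is the DLT rate above which a favourable benefit/risk balance is no longer thought likely.

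**The concern.** The plan allows for a decision about one cohort, but its only numerical rule averages over cohorts. If toxicity is concentrated in one tumour type, the average is pulled down by the others. A reported figure below 33% could then describe a pool that contains a cohort well above the plan's own limit.

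The plan gives reasons to expect differences between tumour types. Section 3.9.1 sets separate transaminase and platelet entry limits for "subjects with hepatocellular cancer": AST/ALT up to 5 x ULN against 3 x ULN, and platelets from 60 against 100 x 10³/µL. Drug-related hepatic events such as "Any Grade ≥ 3 elevation of AST, ALT, or total bilirubin" count as DLTs under Section 4.3.1. Section 1.6 notes that pulmonary inflammation with nivolumab may be numerically greater in NSCLC.

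The planned analyses would not reveal the difference either. Section 8.4.2 tabulates adverse events by treatment, and the synopsis by treatment arm and dose level; neither mentions tumour cohort.

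**Working it through.** **What the plan computes.** Section 8.1.2 gives chances for a 40-subject cohort at a true response rate of 40%. The exact binomial reproduces them: at least 12 responses 0.929 (stated 93%), at least 13 responses 0.871 (87%), 11 or fewer 0.071 (7%). No such figure is given for the toxicity trigger.

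**Inputs.** Six Part D cohorts of 40, so N = 240 (Section 3.1); limit 33% (Sections 3.5 and 3.7). The plan does not say whether the rate counts subjects or events; subjects are counted here.

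**Dilution at full enrolment.**
- Share of one cohort with toxicity in all 40 subjects: 40/240 = 16.7%.
- Events needed to exceed 33%: 0.33 x 240 = 79.2, so 80.
- Rate needed in the other five cohorts: (80 - 40)/200 = 20.0% (break-even (79.2 - 40)/200 = 19.6%).
- Chance that the final aggregate exceeds 33% with one cohort at 100% (exact convolution of two binomials): below 0.01% if the others are at 10%, 3% at 15%, 53% at 20%.
- If Part C were pooled as well, N = 290, the share is 40/290 = 13.8% and 56/250 = 22.4% is needed elsewhere. A wider pool only strengthens the dilution.

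**Before full enrolment.** The rule can fire early. With 40 of 40 affected and no events elsewhere, it is met while at most 81 other subjects have been treated (40/121 = 33.1%; 40/122 = 32.8%). The next table gives the simulated chance that the aggregate rule fires at some point in Part D, with the 240 subjects in random order. The true rates are illustrative assumptions.

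| Checked from subject | One cohort 50%, five 10% | All six cohorts 10% |
|---|---|---|
| 6 | about 33% | about 13% |
| 10 | 16% | 3% |
| 30 | 2% | about 0.1% |

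The first scenario has an overall rate of (40 x 0.5 + 200 x 0.1)/240 = 16.7%. With every cohort at 16.7%, the rule checked from 6 subjects also fires in about 33% of trials. So the aggregate responds to the overall rate and to early noise, and does not single out the affected cohort.

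**A within-cohort check.** Chance of firing in one cohort of 40, looking after every subject from the sixth (exact recursion):

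| True rate | Posterior probability above 0.9 that the rate exceeds 33%, Beta(0.5, 0.5) prior | Raw observed rate above 33% |
|---|---|---|
| 10% | 0.3% | 13% |
| 20% | 5% | 44% |
| 50% | 92% | over 99% |

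The posterior criterion is stricter than a raw 33%: at 40 subjects it needs 18 events (45%). For at least one of six cohorts, using the unrounded 0.31% and 4.7%, it fires in 1 - (1 - 0.0031)^6 = 1.8% at a common rate of 10% and 1 - (1 - 0.047)^6 = 25% at 20%. The raw limit gives 57% and 97%.

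**The case against.** The strongest reply is that the number is not the only safeguard. Section 3.7 sends all safety signals to the Medical Surveillance Team, with ad hoc meetings if needed. Section 8.1.2 bases continued enrolment on the totality of data, Section 1.6 adds regular review by the Medical Monitor and pharmacovigilance, and the study is open-label. The trigger itself only prompts discussion. This stands. A reader might infer that a cohort with toxicity in every subject could pass unreviewed; the documents do not support that. But none of these provisions supplies a cohort-level number, and Section 7 provides no data monitoring committee.

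The rule also applies at any time, so the full-enrolment arithmetic does not show that it can never fire. That stands too. For the same reason, the dilution should not be carried over to Part C. Two cohorts of 25 with 15 and 1 events end at 16/50 = 32%, but over random orderings of those events the running rate passes 33% in 81% of cases when checked from 30 subjects and 94% when checked from 6.

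Two further inferences are tempting and not secure. One is to dilute the pool with the dose-escalation subjects already treated at 240 mg; the rule is introduced as monitoring of the expansion cohorts, and whether earlier subjects count is not stated. The other is that hepatocellular subjects enter with a looser bilirubin limit; in Section 3.9.1 the Cohort 8 criterion (1.5 x ULN) and the organ-function list (below 3 mg/dL) conflict and must be reconciled.

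Finally, in an early-phase study without formal hypotheses, a cohort-level number can be called a design preference. That limits the weight of the point, but Section 3.7 itself foresees the cohort-level decision.

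**Conclusion.** The point holds as a gap in the numerical monitoring, not as a failure of safety oversight. At full enrolment a Part D cohort with toxicity in every subject contributes 16.7%, and the trigger is not met unless the other five reach about 20%. This is arithmetic; it assumes six cohorts of exactly 40, pooled alone, with subjects counted. Sizes are approximate in the plan, so replacements or over-enrolment would shift the figures slightly.

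The early-firing figures also assume random-order accrual and illustrative rates. A fast-enrolling affected cohort would fire the rule sooner. The change is a cheap improvement that the sponsor should make.

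**What to change.** In Sections 3.5 and 3.7 and the synopsis, keep the aggregate trigger and add that the DLT-criteria rate is also tabulated within each expansion cohort against the existing 33% limit. State a minimum number of subjects and an evidence criterion, and say that crossing it prompts the same discussion for that cohort. One example is a posterior probability above 0.9 that the rate exceeds 33%, with a Beta(0.5, 0.5) prior, from 6 subjects. A raw observed 33% should not be used from 6 subjects, because of its false-alarm rate.

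In the same edit, reconcile the synopsis denominator (Part C only) with Sections 3.5 and 3.7, and state which subjects are in the pool and whether subjects or events are counted.

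The cost is protocol wording and one more line per cohort in the running safety table, from data already collected. The downside is a few extra discussions: with the example criterion, 0.3% per cohort at a true 10% and 5% at 20%. If enrolment has already finished, the useful part is to report the rate by cohort beside the aggregate.

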3.6 Dose-limiting Toxicities

For the purpose of guiding dose escalation, DLTs will be defined based on the incidence and grade of AEs for which no alternate cause can be identified (Section 4.3.1). The incidence of DLTs which occur within 4 weeks following the start of study therapy will guide dose escalation decisions. AEs will be graded according to the National Cancer Institute (NCI) Common Terminology Criteria for Adverse Events version 4.03 (CTCAE v4.03). For the purposes of subject management, drug-related AEs occurring at any time which meet the DLT definition will lead to dose interruption and/or permanent discontinuation of study drug as defined in Section 4.3.6.

[figure not shown]
The DLT evaluation interval begins on the first day of treatment and continues for 4 weeks, that is, through Day 28 of the first cycle in both Parts A and B. Subjects discontinued during DLT observation period due to DLT are also considered as DLT evaluable. Based on the predicted human T-HALF of BMS-986156 of 2 weeks, this interval is expected to cover the anticipated time frame for the occurrence of clinically significant immediate and early onset AEs related to (i) single dose BMS-986156 monotherapy or first combination dose with nivolumab and, (ii) repeat dosing of monotherapy BMS-986156 as well as combination dose with nivolumab.

3.6.1 Safety observation time for Q4W dosing

Part E will consist of an initial safety lead in period of up to 12 subjects. Six subjects need to complete the 14 day observation period before the full expansion cohorts, of up to 40 subjects, are opened. Patients who discontinue for reasons other than disease progression, death, or treatment-related toxicity may be replaced. An observation period of 14 days has been chosen based on pharmacokinetic (PK) modeling and simulation for BMS-986156, based on PK parameters derived from preclinical studies. [REDACTED]

In part E, BMS-986156 will be evaluated at a dose of 480 mg every 4 weeks (Q4W) with nivolumab 480 mg Q4W. The BMS-986156 480 mg Q4W dose is much lower than the already assessed safe dose of 800 mg Q2W dose (given as monotherapy and combination with nivolumab 240 mg Q2W). Additionally, PK predictions indicate that BMS-986156 concentrations during the first 2 weeks after treatment with 480 mg Q4W will be higher than those achieved by first 240 mg Q2W dose of BMS-986156 Figure 3.6.1-1. However, BMS-986156 levels after first 480 mg dose will be markedly lower than the C_{max} achieved after 1st or 2nd dose of 240 mg BMS-986156 within 7 days, as indicated by the dotted lines below in Figure 3.6.1-1. A similar trend is expected for nivolumab 480 mg Q4W when compared with nivolumab 240 mg Q2W. Although levels of BMS-986156 and nivolumab with 480 mg Q4W dosing regimens are predicted to be lower than the concentrations achieved after 2nd dose with Q2W dosing within 7 days, an additional 7 day safety margin was included to give a 14 day safety observation period was chosen. This measure ensures that nivolumab concentrations will be well below the C_{max} seen with the tested 240 mg nivolumab plus BMS-986156 combination dose evaluated in part D [REDACTED]. A strict safety monitoring in patients will continue throughout the study.

Figure 3.6.1-1: Predicted BMS-986156 concentrations with Q2W and Q4W dosing using a preliminary pharmacokinetic model

3.7 Stopping Rules During Cohort Expansions

Continuous evaluation of toxicity events in the cohort expansions will be performed throughout enrollment in the expansion cohorts. If at any time, the aggregate rate of treatment-related toxicities meeting DLT criteria exceeds 33% across all subjects treated across all cohorts treated within monotherapy and combination therapy phases at the same dose, the findings will be discussed and further enrollment may be interrupted. If an expansion cohort is discontinued due to toxicity, a new cohort at a previously tested lower dose level, or an alternate treatment regimen (see [Table 3.4.1-1](#)) may be considered based on the aggregate safety experience and in consultation and agreement between Investigators and Sponsor.

All safety signals throughout the conduct of the study will be reviewed by the BMS-986156 Medical Surveillance Team (MST). If unexpected safety findings are identified between scheduled MST meetings, an ad hoc meeting will be convened as appropriate.

Efficacy and safety will be continuously monitored and go/no go decision will be made by discussion with sponsor based on totality of data after assessing benefit/risk ratio in combination with clinical judgement.

